6.1. Screening

The screening phase is the interval between signing the ICF and the day the subject is enrolled in the study (Day 1). The screening phase may not exceed 28 days. Informed consent must be obtained before performing any study-specific procedures not considered SOC.

Procedures conducted as part of the subject's routine clinical management (eg, blood count, imaging studies) and obtained before signing of informed consent may be used for screening or baseline purposes provided the procedure meets the Protocol-defined criteria and has been performed in the timeframe of the study.

Assessments that are required to demonstrate eligibility may be performed over the course of 1 or more days during this phase. Blood chemistry and hematology screening laboratory assessments used to determine subject eligibility must be collected within 14 days before Day 1. Results from the screening visit evaluations will be reviewed by the investigator to confirm subject eligibility before enrollment or the administration of study drug. Tests with results that fail eligibility requirements may be repeated during screening if the investigator believes the results to be in error. For screening assessments that are repeated, the most recent available result before study drug administration will be used to determine subject eligibility.

Additionally, a subject who fails screening may repeat the screening process 1 time if the investigator believes there has been a change in eligibility status (eg, after recovery from an infection).

Additionally, the screening phase will be used to determine the baseline assessments of clinical condition and disease status. Tumor assessments appropriate to the type of malignancy will be performed and recorded in the eCRF.

6.2. Treatment

6.2.1. Day 1

The treatment phase begins on the day the subject receives the first dose of study drug; this is defined as **Day 1** (or Cycle 1 Day 1) and continues until a decision is made to permanently

CONFIDENTIAL

CONFIDENTIAL

discontinue the study drug. At Day 1 (Cycle 1 Day 1), results from screening phase should be reviewed to determine if the subject continues to meet the eligibility requirements as specified in the Protocol. See [Table 7](#), [Table 8](#), [Table 10](#), [Table 11](#), [Table 13](#), [Table 14](#), [Table 16](#), [Table 17](#), [Table 19](#), and [Table 20](#) for discussion of details regarding the laboratory assessments performed at Day 1 (Cycle Day 1). Day 1 (Cycle 1 Day 1) blood chemistry and hematology assessments may be omitted if the screening laboratory samples are collected are within 3 days before Day 1 (Cycle 1 Day 1). If Day 1 (Cycle 1 Day 1) laboratory samples are collected, the blood draws should be performed before administration of first dose of study drug.

6.2.2. Visit Scheduling

Dates for subsequent study visits will be determined based on Day 1 (Cycle 1 Day 1) and should occur within the allotted visit window unless delayed for safety reasons. If study drug or SOC regimen administration must be interrupted at the beginning of a new planned cycle, the cycle will be delayed until the study drug or SOC regimen can be restarted as noted below. All planned assessments are shown in [Table 6](#), [Table 9](#), [Table 12](#), [Table 15](#), and [Table 18](#).

- Visit schedules for Part 3 and Part 4 C-TGA subjects receiving I-DAC will be based on 21-day cycles anchored to the INCB053914 administration. If I-DAC is given as reinduction or consolidation, the regimen start should align with a Day 1 of the 21-day cycle whenever possible.
- Visit schedules for Part 3 and Part 4 C-TGB subjects will be based on the start of subsequent cycles of azacitidine. Should a cycle start be delayed, subjects should continue to receive INCB053914 if appropriate.
- Part 3 and Part 4 C-TGC subjects will be seen every 4 weeks through Week 24 and every 12 weeks thereafter irrespective of whether INCB053914 and/or ruxolitinib are on hold. The study visits (Week 1, Week 2, etc) were named to align with the completion of a week's worth of study drug (ie, Week 1 is planned to occur on Study Day 8, or the end of 1 week of study drug).
- If the optional C-TGA E2 (L-DAC combination) is conducted, visit schedules for these subjects will be based on the start of subsequent cycles of L-DAC. Should a cycle start be delayed, subjects should continue to receive INCB053914 if appropriate.

During the treatment phase, regular study visits (physician visits) and laboratory-only visits will occur as denoted on the respective Schedules of Assessment and Laboratory Assessment tables.

6.3. End of Treatment

When the subject permanently discontinues study drug, the EOT visit should be conducted. If the EOT visit coincides with a regular study visit, the EOT evaluations will supersede those of that scheduled visit, and the data should be entered in the EOT visit in the eCRF. The subject should be encouraged to return for the follow-up visit.

CONFIDENTIAL

CONFIDENTIAL

6.4. Follow-Up

6.4.1. Safety Follow-Up

The safety follow-up phase is the interval between the EOT visit and the scheduled safety follow-up visit. Adverse events and SAEs must be reported up until at least 30 days after the last dose of study drug, the date of the safety follow-up visit, or until study drug-related toxicities resolve, return to baseline, or are deemed irreversible, whichever is longer. Reasonable efforts should be made to have the subject return for this follow-up visit and report any AEs that may occur during this period.

6.4.2. Disease Status Follow-Up

Subjects who discontinue study treatment for a reason other than disease progression will move into the disease status follow-up phase and should be assessed at the intervals specified in [Table 6](#), [Table 9](#), [Table 12](#), and [Table 18](#), using the appropriate disease assessment criteria (Section 7.6) to monitor disease status. Every effort should be made to collect information regarding disease status until 1 of the following:

- Start of new antineoplastic therapy
- Disease progression
- Death
- Withdrawal of consent
- End of the study

[REDACTED]

6.5. Unscheduled Visits

Clinic visits or diagnostic laboratory visits not prescribed in the Protocol may be performed at any time clinically indicated. Results of assessments performed at these visits should be entered as "unscheduled" visits in the eCRF. The sponsor may also request additional visits to be performed, if needed, based on emerging safety data.

7. CONDUCT OF STUDY ASSESSMENTS AND PROCEDURES

7.1. Administration of Informed Consent Form

Valid informed consent must be obtained from the study subject before conducting any study-specific procedures using an ICF approved by the local IRB/IEC that contains all elements required by ICH E6 and describes the nature, scope, and possible consequences of the study in a form understandable to the study subject. Local and institutional guidelines for ICF content and administration must be followed; the original signed ICF must be retained by the investigator and a copy of the signed ICF must be provided to the study subject. The informed consent process for each subject must be documented in writing within the subject source documentation. Subjects of childbearing potential must agree to take appropriate measures to avoid pregnancy in order to participate in the study (see [Appendix A](#)).

7.2. Interactive Response Technology Procedure

The interactive response technology (IRT) will be contacted to obtain a subject ID number when a subject enters the screening phase. Additionally, the IRT will be contacted at each visit at which study drug is dispensed to update the study drug supply and upon the decision to discontinue treatment. Refer to the IRT manual for detailed instructions.

7.3. Demography and Medical History

7.3.1. Demographics and General Medical History

Demographic data and a complete medical and medication history will be collected at screening. This will include date of birth, race, ethnicity, and medical and surgical history for the disease under study. Details regarding the disease for which the subject has enrolled in this study (eg, date of diagnosis, primary tumor histology, prior systemic therapies, surgeries, radiation therapy, and stage of cancer) will be recorded separately and not listed in medical history.

7.3.2. Transfusion History Status (Ruxolitinib Combination Cohorts Only)

All transfusions of red blood cell products or platelets from at least 16 weeks before the screening visit will be recorded. The product(s) delivered, date of transfusion, and units delivered will be recorded on the CRF.

7.3.3. Screening Symptom Form (Ruxolitinib Combination Cohorts Only)

In order to satisfy inclusion criteria for Part 3 C-TGC and Part 4 C-TGC E1, active symptoms of MF at the screening visit as demonstrated by presence of 1 symptom score ≥ 5 or 2 symptom scores ≥ 3 using the Screening Symptom Form ([Appendix O](#)) will be recorded on the CRF.

7.4. Prior and Concomitant Medications and Procedures

Prior and concomitant medications and procedures will be reviewed to determine subject eligibility. All concomitant medications and measures must be recorded in the eCRF, and any medication received or procedures performed within 30 days before the first dose and through

CONFIDENTIAL

CONFIDENTIAL

the safety follow-up period will be recorded in the eCRF. The medication record will be maintained after signing the ICF to document concomitant medications, including any changes to the dose or regimen. Concomitant medications include any prescription, over-the-counter, or natural/herbal preparations taken or administered during the study period. Concomitant treatments and/or procedures that are required to manage a subject's medical condition during the study will also be recorded in the eCRF.

7.5. Safety Assessments

7.5.1. Adverse Events

Adverse events will be monitored from the time the subject signs the ICF. Subjects will be instructed to report all AEs during the study and will be assessed for the occurrence of AEs throughout the study. In order to avoid bias in eliciting AEs, subjects will be asked general, nonleading questions such as "How are you feeling?" All AEs (serious and nonserious) must be recorded on the source documents and eCRFs regardless of the assumption of a causal relationship with the study drug. The definition, reporting, and recording requirements for AEs are described in Section 8.

If a subject experiences a treatment-emergent rash, photographic images of the rash should be collected and retained as part of the subject's medical record. De-identified copies of the images should be submitted to the sponsor at its request so the character of the rash can be better evaluated.

7.5.2. Physical Examinations

7.5.2.1. Comprehensive Physical Examination

Physical examinations must be performed by a medically qualified individual such as a licensed physician, physician's assistant, or an advanced registered nurse practitioner, as local law permits.

The comprehensive physical examination will include assessment(s) of the following organ or body systems: skin; head, eyes, ears, nose, and throat; thyroid; lungs; cardiovascular system; abdomen (liver, spleen); extremities; and lymph nodes; as well as a brief neurological examination.

7.5.2.2. Targeted Physical Examination

The targeted physical examination will be a symptom-directed evaluation conducted by the investigator or a medically qualified designee. The targeted physical examination will include assessment(s) of the body systems or organs, as indicated by subject symptoms, AEs, or other findings.

7.5.3. Vital Signs

Vital sign measurements include blood pressure, pulse, respiratory rate, body temperature, height (at screening), and body weight. Blood pressure and pulse will be taken with the subject in the recumbent, semirecumbent, or sitting position after 5 minutes of rest.

CONFIDENTIAL

CONFIDENTIAL

7.5.4. Electrocardiograms

7.5.4.1. Twelve-Lead Electrocardiograms

A central ECG vendor will be used. The 12-lead ECGs will be interpreted by the investigator at the site for immediate subject management. The trace will also be transmitted to the central ECG vendor for analysis by a central reader, and data archiving. The decision to include or exclude a subject or withdraw a subject from the study based on an ECG flagged as "Abnormal, Clinically Significant" is the responsibility of the investigator, in consultation with the sponsor's medical monitor, as appropriate. Any treatment-emergent ECG finding occurring on study that is abnormal and clinically significant in the judgment of the investigator should be reported as an AE.

7.5.4.2. Electrocardiogram Procedures

All 12-lead ECGs will be performed with the subject in a recumbent position after 5 minutes of rest and should not be performed within 15 minutes after a blood collection.

7.5.4.3. Additional Instruction for Timed Electrocardiograms

Timed ECGs will be conducted before the clinic administration of study drug (predose) and using the schedule shown in Electrocardiograms conducted before administration (establishing the baseline for the day) should be performed in triplicate ([Table 8](#)). The ECGs should be conducted before, but within 15 minutes of, the PK blood collection at the corresponding timepoint. The specified postdose timepoints may be adjusted based on emerging PK data.

7.5.5. Laboratory Assessments

7.5.5.1. Chemistry, Hematology, Urinalysis, Liver Function Panel, Coagulation Panel, and Hepatitis Screening

Chemistry, hematology, liver function panel, coagulation panel, and hepatitis screening will all be analyzed by the local site laboratory. The investigative site will enter the local laboratory results and laboratory normal ranges into the eCRF. All local laboratory assessments (ie, blood chemistries, hematology assessments, LFTs, coagulation tests, lipid testing, and urinalysis) should be performed using standard procedures on the days indicated in [Table 7](#), [Table 10](#), [Table 13](#), [Table 16](#), and [Table 19](#). [Table 5](#) lists additional timepoints for increased frequency of LFT panel and coagulation panel assessments should subjects experience treatment-emergent liver enzyme elevations. [Table 21](#) lists the required laboratory tests in each category; additional testing may be required by the sponsor based on emerging safety data. Additional tests may also be performed if clinically indicated.

Blood chemistry (including LFTs) and hematology screening assessments used to determine subject eligibility must be collected within 14 days before Cycle 1 Day 1. On Day 1, laboratory data from the screening evaluations must be reviewed to confirm eligibility. Cycle 1 Day 1 blood chemistry, hematology, LFT, and coagulation assessments may be omitted if the screening laboratory samples are collected within 3 days before Cycle 1 Day 1. If Cycle 1 Day 1 laboratory samples are needed, they must be collected before administration of the first dose of study drug. After Cycle 1, predose laboratory procedures can be conducted up to 72 hours

CONFIDENTIAL

CONFIDENTIAL

before study drug administration (within the 3-day study window), and results should be reviewed by the investigator or qualified designee and found to be acceptable before a new cycle of treatment is initiated.

7.5.5.2. Pregnancy Testing

A serum pregnancy test will be required for all women of childbearing potential before first dose of study drug as shown in [Table 7](#), [Table 10](#), [Table 13](#), [Table 16](#), and [Table 19](#). Subsequently, pregnancy tests (either serum or urine) may be conducted as medically indicated or as required per local guidelines.

7.5.5.3. Hepatitis Screening Tests

Testing for hepatitis (detailed in [Table 21](#)) is required at screening, and results should be reviewed before Day 1 to confirm eligibility. Due to the risk of seroconversion with ruxolitinib treatment, hepatitis B and C viral loads by PCR assay will be required for all ruxolitinib combination cohort subjects. However, for all other subjects, additional testing for HBV-DNA and HCV-RNA by PCR assay to further assess hepatitis status will only be required if hepatitis B and/or C serology are positive. Additionally, HBV-DNA does not need to be performed if the HBV surface antibody is the only positive result (indicating immunity due to vaccination).

[figure not shown]
The eligibility of any subject with positive viremia (eg, PCR assay targets detected) must be discussed with the medical monitor before subject enrollment.

[figure not shown]
Generally hepatitis serology tests should be submitted early in the screening process because of the length of time frequently needed to obtain the results.

7.6. Efficacy Assessments

[figure not shown]
[figure not shown]
The following disease response criteria will be used for each of the malignancies included in this study:

- Acute myeloid leukemia: International Working Group Response Criteria for Acute Myeloid Leukemia ([Cheson et al 2003](#); [Appendix D](#))

[figure not shown]

Treatment cycles may be delayed; therefore, disease response assessments may be delayed as well to synchronize with treatment cycles. A disease assessment may be performed as an unscheduled procedure if clinically indicated. For subjects who discontinue treatment for reasons other than disease progression, every effort should be made to continue monitoring their disease status until start of new anticancer therapy, documented disease progression, death, or the end of the study, whichever occurs first.

[figure not shown]
CONFIDENTIAL

CONFIDENTIAL

**7.6.3. AML, [REDACTED]
[REDACTED] Bone Marrow Examination**

Bone marrow examination (aspirate and biopsy) is required at screening for subjects with diseases that are typically monitored through bone marrow examination, including AML, [REDACTED] [REDACTED] (bone marrow examination may be omitted with approval of the medical monitor).

In the combination cohorts (Parts [REDACTED] 4), if disease status requires assessment with bone marrow aspirate or biopsy, subjects with AML, [REDACTED] [REDACTED] should have a bone marrow aspirate and/or biopsy performed after 1 cycle of therapy (or earlier if clinically indicated), Month 2, and then approximately every 2 months thereafter. Specific requirements for bone marrow examination of each combination cohort are included in the footnotes of each respective table (Section 6). Subjects without circulating blasts at the screening hematology assessment may use a historical biopsy obtained within 60 days before Cycle 1 Day 1 (Day 1), and all data and reports are available for investigator's review.

Samples of bone marrow biopsy and aspirate will be set to Incyte or its designee for additional immune and molecular profiling.

CONFIDENTIAL

CONFIDENTIAL

Data from the pathology report result from the bone marrow examination will be captured in the eCRF. All bone marrow examinations should include a unilateral aspiration and biopsy with FISH and cytogenetic testing, when feasible. Subjects may be enrolled based on a biopsy only when a "packed marrow" precludes aspiration at the decision of the medical monitor. Results of assessments performed under SOC before the signing of informed consent may be used as the baseline disease assessment in lieu of a study-specific procedure if performed within 60 days of the first dose of study drug (Cycle 1 Day 1) and if adequate archive material is available and there has been no anticancer therapy in the interim.

Reference Section 7.9.1 for more information on tissue collection.

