Bone marrow examination ^k	7.9.1	X	X ^j									
Immunophenotyping ^l	7.6.5	X	When confirming CR									
Provide reminder cards	7.10.2	X	X	X	X	X	X	X				
Poststudy disease status	6.4.2									X		

CR = complete remission.

^a From Cycle 4 onward, subjects are only required to receive azacitidine at the investigative site on Day 1 of each cycle. All other azacitidine doses and study assessments may be performed at a local clinic. Day 8 assessments are not required beginning with Cycle 4. Data from local clinic assessments do not need to be entered into the CRF.

^b Day 22 assessments are performed in Cycle 1 only.

CONFIDENTIAL

CONFIDENTIAL

- ^c If subjects have not sufficiently recovered from chemotherapy-related toxicities after 28 days, they should be seen weekly until such time that a subsequent cycle can be started. These visits should be entered as unscheduled visits in the eCRF. If subjects cannot start a subsequent cycle within 42 days, the site should contact the medical monitor.
- ^d Azacitidine will be administered as 75 mg/m² SC or IV for 7 days during 9-day or less period (ie, a 2-day break allowed on weekend, if needed) of 28-day cycle.
- ^e All study drug for Cycle 1 will be dispensed at Cycle 1 Day 1; subject will bring unused study drug to clinic for compliance check on Cycle 1 Day 15. Drug will only be dispensed at Day 1 of all subsequent cycles and compliance will be checked at the start of the next subsequent cycle.
- ^f Compliance check only.
- ^g If needed.
- ^h Height measured at screening only. Weight required at screening, Day 1 of each cycle, EOT, and the follow-up visit.
- ⁱ Subjects must be followed for AEs for 30 days (+ 5 days) after the EOT visit (or after the last dose of study drug if the EOT visit was not performed).
- ^j Bone marrow biopsy and/or aspirates for response is to be performed at Cycle 4 Day 1 or earlier as clinically indicated, followed by every other month as clinically indicated, or upon circulating blood cell recovery to assess antileukemic activity (cytogenetic testing is not required if CR is not presented). Note: For subjects who have a significant blast count reduction (as determined by the investigator) but have not completely cleared circulating blasts, the Cycle 4 Day 1 bone marrow is still strongly encouraged to be performed to assess the impact of treatment on the bone marrow blast content. See Section 7.6 for additional details.

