9.5. Interim Analysis

In Part 4, there are up to 3 planned interim analyses for futility in C-TGA E1, C-TGB E1, and an optional C-TGA E2. The Simon 2-stage design will be applied to each expansion cohort independently. During Stage 1, 13 subjects will be enrolled into each expansion cohort. If 3 or fewer of the first 13 evaluable subjects achieve an objective response, the cohort will be terminated for futility. In any cohort that exceeds this number of responders, additional subjects will be enrolled for Stage 2 evaluation.

CONFIDENTIAL

CONFIDENTIAL

Based on this early termination rule, the probability of early termination is 0.7473 under the assumption of historical control response rate; the probability of early termination is 0.1686 under the assumption of desired response rate.

The interim analysis for each expansion cohort will be conducted once the first postbaseline bone marrow biopsies for Stage 1 subjects within the cohort are available. Enrollment will be held at that time unless a sufficient number of responders (> 3 responders) have been observed before that time.

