4.1.5. Cycle Length and Duration

Cycle 1 Day 1 is the day that the first dose of study drug is administered. For monotherapy, the scheduled cycle length is 21 days for Parts 1 and 2 (all treatment groups/cohorts). For combination therapy, the scheduled cycle length is 21 days for the Part 3 C-TGA, Part 3 C-TGC, Part 4 C-TGA E1, and Part 4 C-TGC E1 cohorts and 28 days for the Part 3 C-TGB, Part 4 C-TGA E2, and Part 4 C-TGB E1 cohorts.

Actual Day 1 of subsequent cycles will correspond with the first day of administration of INCB059314 or standard-of-care agent in that cycle; thus, treatment cycles may become out of sync with the originally planned schedule, and cycle length may be different from 21 or 28 days. The date of the Day 1 of subsequent cycles recorded in the eCRF will be used as the Day 1 of subsequent cycles.

In the Part 3 C-TGA and Part 4 C-TGA E1 (cytarabine) cohorts, cytarabine treatment will be administered in 3 possible periods anchored to the 21-day INCB053914 cycles.

- **First Induction Cycle:** Subjects will initially receive a 21-day induction cycle.
- **Second Induction Cycle (optional):** At the discretion of the investigator, a second induction cycle may be started between 15 days and 8 weeks after initiation of Cycle 1 in subjects with residual leukemia upon bone marrow assessment during initial induction. Treatment in the second induction cycle may not initiate until all drug-related toxic effects have resolved to \leq Grade 1.
- **Consolidation Phase:** At the discretion of the investigator, up to 2 additional cycles may be given as consolidation therapy in subjects who achieve complete remission or CRp recovery.

The start of subsequent induction or consolidation cycles of I-DAC should be coordinated with the Day 1 of a 21-day INCB053914 cycle when feasible.

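### The C-TGB E1 futility look is keyed to the first post-baseline marrow with no named visit or minimum follow-up, so it can be taken before all eventual responders are visible

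*Protocol*

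**What the plan says.** **When the look happens.** Protocol 9.5 says that the interim analysis for each AML expansion cohort "will be conducted once the first postbaseline bone marrow biopsies for Stage 1 subjects within the cohort are available". Protocol 9.4.1 and SAP 11 use the same trigger. None of the three names a visit, a cycle or a minimum follow-up.

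**What the look decides.** "If 3 or fewer of the first 13 evaluable subjects achieve an objective response, the cohort will be terminated for futility". Protocol 9.5 holds enrollment at that point unless more than 3 responders have already been seen.

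**When the first marrow is due.** Protocol 7.6.3 gives a general schedule for the combination cohorts. It is conditional ("if disease status requires assessment with bone marrow aspirate or biopsy") and says that AML subjects "should have a bone marrow aspirate and/or biopsy performed after 1 cycle of therapy (or earlier if clinically indicated), Month 2", then about every 2 months. The next sentence reads "Specific requirements for bone marrow examination of each combination cohort are included in the footnotes of each respective table (Section 6"). The opening of Section 6 likewise sends every assessment to the table for the subject's regimen. For azacitidine that is Table 12, whose footnote j says "Bone marrow biopsy and/or aspirates for response is to be performed at Cycle 4 Day 1 or earlier as clinically indicated". Repeat marrows come at two-month intervals after that, where there is a clinical reason.

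**How response is scored.** SAP 7.4.1.2.1 uses the best response recorded up to and including the first treatment failure, relapse or progression. Later marrows can therefore add responders.

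**The concern.** The Simon design in Protocol Table 23 treats the 13 Stage 1 outcomes as final when they are counted. The trigger wording does not secure that. It attaches the count to whichever marrow comes first, and footnote j allows that marrow to come before Cycle 4 Day 1. A site that follows the general sentence in 7.6.3 and takes a marrow after Cycle 1 breaks neither passage.

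A subject who has had one azacitidine cycle and is not yet in CR or CRi may still reach it later, and the SAP would then score that subject as a responder. A cohort stopped on an early count cannot be reopened by those later marrows. What is at stake is the chance of stopping an active combination, and a Stage 1 count that mixes subjects assessed at different times.

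**Working it through.** **Inputs.** Stage 1 n1 = 13, stop at r1 = 3 or fewer; total n = 43, so 30 in Stage 2; success needs more than r = 12; p0 = 20%, p1 = 40% (Protocol Table 23, SAP Table 1). SAP 4.1.5 sets the cycle length: "28 days for the Part 3 C-TGB, Part 4 C-TGA E2, and Part 4 C-TGB E1 cohorts".

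**Step 1. Reproduce the plan's figures.**
- Early stop = P(Bin(13, p) ≤ 3).
- At 40%: 0.0013 + 0.0113 + 0.0453 + 0.1107 = 0.1686, as stated.
- At 20%: 0.7473, as stated.
- P(success) = Σ over x = 4 to 13 of P(Bin(13, p) = x) × P(Bin(30, p) ≥ 13 − x). This gives 0.0496 at 20% and 0.8002 at 40%, in line with the stated 0.05 and 80%.

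**Step 2. Dates, per subject.**
- After 1 cycle: 1 + 28 = Day 29.
- Cycle 4 Day 1: 1 + 3 × 28 = Day 85.
- Table 12 lets a cycle stretch: "If subjects cannot start a subsequent cycle within 42 days, the site should contact the medical monitor". With three 42-day cycles, Cycle 4 Day 1 is 1 + 3 × 42 = Day 127.

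**Step 3. Effect of an early count.** Let f be the fraction of eventual responders already visible at the look. The documents give no time-to-response figure, so f is an assumption. The final analysis is taken to count all eventual responders.

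*Case A: f applies to all 13 subjects.*
- Early stop = P(Bin(13, p·f) ≤ 3).
- P(success) = Σ over x of P(Bin(13, p) = x) × P(Bin(x, f) ≥ 4) × P(Bin(30, p) ≥ 13 − x).

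*Case B: 9 subjects are fully followed and f applies only to the last 4* (the split is also an assumption). Let A ~ Bin(9, p), E ~ Bin(4, p), S ~ Bin(E, f) and Y ~ Bin(30, p). The cohort stops if A + S ≤ 3. It succeeds if it continues and A + E + Y ≥ 13.

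| Case | f | Early stop at 40% | Power at 40% | Type I error at 20% |
|---|---|---|---|---|
| Plan | 1 | 0.169 | 0.800 | 0.050 |
| A | 0.9 | 0.254 | 0.722 | 0.041 |
| A | 0.75 | 0.421 | 0.564 | 0.028 |
| B | 0.75 | 0.23 | 0.74 | 0.043 |
| B | 0.5 | 0.30 | 0.68 | 0.037 |

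As a check on one row, case A with f = 0.75 uses p·f = 0.30, and 0.0097 + 0.0540 + 0.1388 + 0.2181 = 0.4206.

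**The case against.** The strongest reply is that the plan already settles the schedule. Section 7.6.3 is general and conditional, its next sentence hands the specifics to the table footnotes, and Section 6 does the same. On that reading Table 12 governs C-TGB E1 and the scheduled response marrow is Cycle 4 Day 1. This largely stands. A reader might infer an unresolved either/or, with the look falling at week 4 or week 12, but the documents do not support that. Those are also times for one subject. The date of the cohort's look depends on accrual and on the last of the 13 Stage 1 subjects, and subjects enrolled earlier will have longer follow-up.

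A second reply is that the trigger says when the look happens, not how subjects are scored, and that SAP 7.4.1.2.1 already uses best response. That is fair for the final analysis. It does not help at Stage 1, because the stop is decided on what has been recorded by then, and nothing says that a subject without CR/CRi at an early marrow is still pending.

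A third reply concerns size. A reader might take a low f for all 13 subjects and infer that power collapses; f = 0.5 in case A would give 0.25. That supposes that all 13 are counted on an immature marrow and that half of the responses come later. The documents support neither assumption.

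**Conclusion.** The point holds in a limited form and is a cheap improvement to a decision rule. Deference to Table 12 fixes the scheduled visit but does not close the gap, because footnote j permits earlier marrows and the look is tied to the first one. The stated 0.1686 and 80% are correct as arithmetic, and they apply only if every eventual responder is visible at the look.

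The size of any loss is unknown. Under the assumptions shown, power at a 40% response rate runs from 0.72 to 0.56 if all 13 subjects are affected (f from 0.9 to 0.75), and from 0.74 to 0.68 if only the last 4 are (f from 0.75 to 0.5). The error is in one direction: wrongful stopping becomes more likely, while Type I error stays at or below the plan's 0.0496. The rule that lets enrollment go on once more than 3 responders are seen limits the harm only where responses come early. Which marrow schedule is clinically right is not judged here.

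**What to change.** 1. Reconcile Protocol 7.6.3 with Table 12 footnote j, so that one response-marrow schedule applies to C-TGB.
2. In Protocol 9.4.1 and 9.5 and in SAP 11, state that a Stage 1 subject counts as a non-responder only after completing the cohort's scheduled response marrow in the reconciled schedule, or after treatment failure, progression, death or leaving treatment without CR/CRi.
3. In the same places, state that an earlier marrow without CR/CRi does not close the subject's score.
4. Leave as written the rule that enrollment continues once more than 3 responders have been seen.

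The change is wording only and leaves the Simon boundaries alone. Its cost is time: the futility decision waits for the last Stage 1 subject's scheduled marrow. If Table 12 governs, that is about 8 weeks later than an after-Cycle-1 look (Day 85 − Day 29 = 56 days), and longer if cycles are delayed. Enrollment may be on hold for that period.
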